3.1. Definitions of Abbreviations

| Abbreviation | Description |
|--------------|--|
| PMS system | CCI [REDACTED] (name of the system supplied by PPD [REDACTED] for managing the progression of post-marketing surveillances) |
| BMI | Body Mass Index |
| AE | Adverse Event |
| SOC | System Organ Class |
| PT | Preferred Term |
| LLT | Low Level Term |

3.2. Definitions of Terms

| Term | Description |
|-----------------------------|--|
| Finalized patient | For Benet Tablets, a finalized patient is defined as a patient who has the date of CRF approval in the PMS system. For Actonel Tablets, a finalized patient is defined as a patient who has the date of temporary finalization in the business management system. |
| Adverse event (AE) | All events entered into the column of [Adverse event] in the case report form (CRF) Any unfavorable or unintended sign (e.g., abnormal laboratory finding), symptom, or disease temporally associated with the use of Benet/Actonel, whether or not it is considered related to Benet/Actonel |
| Adverse drug reaction (ADR) | All adverse events except those not related to Benet/Actonel according to “Causal relationship to Benet/Actonel” both in the column of [Adverse event] in the CRF and determined by the company |
| Serious adverse event (SAE) | Adverse event assessed as serious according to “Seriousness” at least either in the column of [Adverse event] in the CRF or determined by the company, including AEs in Takeda Medically Significant AE List |

3.3. Statistical Arrangements

1) Summary statistics

For quantitative variables, summary statistics are number of relevant patients, mean, standard deviation, minimum, median, and maximum.

2) Number of digits to be displayed

Proportions will be displayed to one decimal place by rounding.

Minimum and maximum will be displayed with the same number of digits as the number of significant figures, and the other summary statistics will be displayed to one lower digit than raw data by rounding.

Statistical p-value will be displayed to four decimal places by rounding. P-value less than 0.0001 will be displayed as <0.0001. Infeasibility of testing will be indicated as “-.”

3) 95% confidence interval

For continuous variables, 95% confidence interval for mean difference will be presented as confidence limits following t-distribution.

4) Rules of statistical testing

One-sample t-test or one-sample Wilcoxon test will be used for pre- and post-treatment comparison of continuous variables.

McNemar test will be used for pre- and post-treatment comparison of ratios.

A two-sided 5% level of significance will be used.

The category of “unknown” will be excluded from statistical testing.

4. Analysis Sets

4.1. Enrolled Patients

All patients for whom the patient registration form has been accepted

4.2. Patients with the CRF Collected

Patients for whom the CRF has been collected before the end of the unit surveillance period and finalized

4.3. Patients Included in Safety Analysis

All patients with the CRF collected, excluding those who meet any of the following criteria:

- 1) Not treated with Benet/Actonel
- 2) Unknown whether an AE occurred
- 3) Deviated from the registration criteria
 - Treated before conclusion of a contract
 - Not registered in the registration period
 - Failed to fax the patient registration form within 15 days after the start of Benet/Actonel treatment

4.4. Patients Included in Efficacy Analysis

All patients included in safety analysis, excluding those who meet any of the following criteria:

- 1) No evidence of 1 to 4 fractures from the fourth thoracic vertebra to the fourth lumbar vertebra provided by thoracic and lumbar spinal radiography performed before the start of the surveillance
- 2) Not 50 years or older
- 3) Not an outpatient who can walk
- 4) Pre- and post-baseline values of all efficacy endpoints (bone turnover markers, bone mineral density, vertebral fracture, non-vertebral fracture, height, and low back pain) are unknown, including incalculable values

5. Handling of Data

Handling of data for analysis is described below. Details of processing will be specified in separately prepared analysis data set specifications.

5.1. Handling of Dichotomous Variables

For dichotomous variables, the presence or absence will be determined as described below when there is a column for details to be specified for “Yes.”

- 1) “Yes” when details are specified
- 2) “No” when no details are specified and “No” is checked
- 3) “Unknown” when neither 1 nor 2) is applicable

5.2. Handling of Adverse Events

When multiple AEs of the same LLT are reported in the same patient, an AE to be employed will be determined as described below.

- 1) AEs that differ in the causal relationship to Benet/Actonel will be handled separately.
- 2) When multiple AEs of the same causal relationship to Benet/Actonel are reported, the most serious AE will be employed.
- 3) When multiple AEs of the same seriousness are reported, the earliest AE will be employed.
- 4) When multiple AEs are reported on the same day, an AE with the latest outcome will be employed.

5.3. Handling of Missing Data

In principle, no missing data will be imputed.

For frequency tabulation of qualitative variables, missing data will be handled as “unknown.” For summary statistics of quantitative variables, missing data will be excluded, and non-missing data will be used.

5.4. Handling of Time Points of Assessment

Data within the permissible range as shown below will be employed.

If there are multiple pieces of data within the permissible range, data on the day closest to the nominal day will be employed. If deviation is the same before and after the nominal day, the latest data will be employed.

<Time points of assessment of vertebral fracture and non-vertebral fracture>

| Time point of assessment | Permissible range | Nominal day |
|-------------------------------|-------------------|-------------|
| Before the start of treatment | Days -90 to 1 | Day 1 |
| Month 6 | Days 2 to 270 | Day 180 |
| Month 12 | Days 271 to 540 | Day 360 |
| Month 24 | Days 541 to 900 | Day 720 |
| Month 36 | Days 901 to 1170 | Day 1080 |
| Final assessment | Days 2 to 1170 | - |

<Time points of assessment of bone turnover markers, bone mineral density, and low back pain>

| Time point of assessment | Permissible range | Nominal day |
|-------------------------------|-------------------|-------------|
| Before the start of treatment | Days -30 to 1 | Day 1 |
| Month 3 | Days 2 to 105 | Day 90 |
| Month 6 | Days 106 to 270 | Day 180 |
| Month 12 | Days 271 to 450 | Day 360 |
| Month 18 | Days 451 to 630 | Day 540 |
| Month 24 | Days 631 to 810 | Day 720 |
| Month 30 | Days 811 to 990 | Day 900 |
| Month 36 | Days 991 to 1170 | Day 1080 |
| Final assessment | Days 2 to 1170 | - |

<Time points of assessment of height>

| Time point of assessment | Permissible range | Nominal day |
|-------------------------------|-------------------|-------------|
| Before the start of treatment | Days -30 to 1 | Day 1 |
| Month 12 | Days 2 to 540 | Day 360 |
| Month 24 | Days 541 to 900 | Day 720 |
| Month 36 | Days 901 to 1170 | Day 1080 |
| Final assessment | Days 2 to 1170 | - |

5.5. Derived Variables

| Derived variable | Description |
|---|--|
| Flag for enrollment | It is identified whether a patient is enrolled. |
| Flag for CRF collection | It is identified whether the CRF for a patient is collected. |
| Flag for inclusion in/exclusion from safety | It is identified whether a patient is included in safety analysis. |
| Flag for inclusion in/exclusion | It is identified whether a patient is included in efficacy analysis. |

| Derived variable | Description |
|--|--|
| from efficacy | |
| Age (years) | Age on the start day of Benet/Actonel treatment; or age described on the [Cover] in the CRF if date of birth is missing |
| BMI (kg/m ²) | Body mass index calculated as body weight (kg) ÷ height (m) ² |
| Duration of disease (years) | Number of years from diagnosis of osteoporosis to the start date of Benet/Actonel treatment (by rounding down) |
| Start date of Benet/Actonel treatment | Date described as the date of the scheduled first dosing on the [Cover] in the CRF; or the earliest (smallest) date among dates described in the [Treatment status of Benet/Actonel] if the first dose is not given as scheduled |
| End date of Benet/Actonel treatment | 30 days after the latest (largest) date among dates described in the [Treatment status of Benet/Actonel] in the CRF |
| Duration of Benet/Actonel treatment (days) | Number of days from the start date of Benet/Actonel treatment to the end date of Benet/Actonel treatment |
| Duration of Benet/Actonel treatment (months) | Number of months from the start date of Benet/Actonel treatment to the end date of Benet/Actonel treatment |
| Number of doses of Benet/Actonel | Total number of doses during Benet/Actonel treatment counted as the number of checks made to “Took the drug” for patient’s treatment status in the [Treatment status of Benet/Actonel] in the CRF |
| Amount of Benet/Actonel administered (mg) | Total dose during Benet/Actonel treatment calculated as number of doses of Benet/Actonel × 75 mg |
| Treatment compliance rate (%) | Percentage of the number of doses taken as instructed by a physician relative to the number of doses indicated by the physician |
| Dosing interval (days) | Number of days from the date of a certain dosing to the date of the next dosing |
| Flag for previous treatment | A drug deemed as previous treatment is identified. |
| Flag for concomitant medication | A drug deemed as concomitant medication is identified. |
| Flag for osteoporosis drug | An osteoporosis drug is identified. |
| Flag for anti-inflammatory analgesic | An anti-inflammatory analgesic is identified. |

| Derived variable | Description |
|--|---|
| Flag for cardiovascular drug | A cardiovascular drug is identified. |
| Flag for central nervous system drug | A central nervous system drug is identified. |
| Flag for antidiabetic | An antidiabetic is identified. |
| Flag for digestive system drug | A digestive system drug is identified. |
| Flag for other drug | Other drug not listed above is identified. |
| Flag for Benet/Actonel 2.5 mg | A drug that is Benet/Actonel 2.5 mg is identified. |
| Flag for Benet/Actonel 17.5 mg | A drug that is Benet/Actonel 17.5 mg is identified. |
| Flag for bisphosphonate other than Benet/Actonel | A bisphosphonate other than Benet/Actonel is identified. |
| Flag for calcium | A drug that is calcium is identified. |
| Flag for vitamin D | A drug that is vitamin D is identified. |
| Flag for osteoporosis drug not listed above | A drug that is an osteoporosis drug not listed above is identified. |
| Flag for steroid | A drug that is a steroid is identified. |
| Number of days to measurement (days) | Number of days from the start date of Benet/Actonel treatment to the date of measurement of the relevant endpoint |
| Time point of assessment (for analysis) | Time points of assessment are reallocated for analysis as specified in Section 5.4, “Handling of Time Points of Assessment.” |
| Flag for employment of data | It is identified whether measurement data are employed. |
| Flag for event | A patient with event is defined as a patient who experienced at least one event such as vertebral fracture. A patient with no event is defined as a patient who experienced no event. |
| Time point of event onset | Time point of event onset is defined as the first onset of event such as vertebral fracture. Time point of event onset is final assessment for patients with no event. |
| Measured value at the start of treatment | The measured value at the start of treatment is identified. |
| Change | Value obtained by deducting the measured value at the start of treatment from a measured value at each time point |
| Percent change (%) | Value obtained by dividing a change by the measured value at the start of treatment and then multiplying the division by 100 |

| Derived variable | Description |
|---------------------------------------|--|
| Time of onset (days) | Number of days from the start date of Benet/Actonel treatment to the date of onset of AE |
| Flag for inclusion/exclusion as an AE | It is identified whether an event is an AE. |
| Relationship (for analysis) | It is identified whether an AE is related to Benet/Actonel. |
| Seriousness (for analysis) | It is identified whether an AE is serious. |
| Novelty | It is identified whether an AE is expected (known) or unexpected (unknown) based on the precautions for Benet/Actonel. |
| Presence or absence of an AE | It is identified whether there is an AE (including “unknown”). |
| Presence or absence of an ADR | It is identified whether there is an ADR (including “unknown”). |
| Presence or absence of a SAE | It is identified whether there is a SAE (including “unknown”). |

6. Analysis Plan

Analysis sets, analysis items, and analysis methods are shown below. Details of variables for analysis and display will be specified in separately prepared statistical analysis specifications.

6.1. Analysis of Patients

6.1.1. Patient Composition Diagram

- 1) Analysis set Enrolled patients
- 2) Chart plan Figure 1-1
- 3) Analysis items
 - Number of registration sites
 - Number of enrolled patients
 - Number of patients with no CRF collected (including reasons for collecting no CRF)
 - Number of patients with the CRF collected
 - Number of patients excluded from safety analysis (including reasons for exclusion)
 - Number of patients included in safety analysis
 - Number of patients excluded from efficacy analysis (including reasons for exclusion)
 - Number of patients included in efficacy analysis
- 4) Analysis methods The number of patients (number of sites) will be calculated for the

analysis item, and a composition diagram will be prepared.

6.1.2. Patient Baseline Characteristics

| | |
|-------------------|---|
| 1) Analysis set | Patients included in safety analysis Patients included in efficacy analysis |
| 2) Chart plan | Table 1-2 |
| 3) Analysis items | Sex [male, female] Age (years) [*] [<50, ≥50 to <65, ≥65 to <75, ≥75], [<60, ≥60 to <70, ≥70 to <80, ≥80], [<65, ≥65] Height at the start of treatment (cm) [*] [<140, ≥140 to <160, ≥160] Body weight (kg) [*] [<40, ≥40 to <50, ≥50 to <60, ≥60] BMI (kg/m ²) [*] [<18.5, ≥18.5 to <25.0, ≥25.0] Disease to be treated [osteoporosis: primary, osteoporosis: secondary] Duration of disease (years) [*] [<1, ≥1 to <5, ≥5] Predisposition to hypersensitivity [no, yes] Concurrent illness [no, yes] |

Disposition of concurrent illness [locomotor disease other than osteoporosis (spinal osteoarthritis, lumbago, spinal column stenosis, osteoarthritis), lifestyle-related disease (diabetes, hypertension, dyslipidemia, chronic obstructive pulmonary disease), cardiac disease (angina pectoris, myocardial infarction, arrhythmia), renal disease (diabetic nephropathy, glomerulonephritis, nephrotic syndrome), hepatic disease (chronic hepatitis, hepatic steatosis, hepatic cirrhosis), digestive disease (esophageal ulcer, gastric ulcer, duodenal ulcer, esophagitis), other (rheumatoid arthritis, other)]

Medical history (except previous fracture) [no, yes]

Disposition of medical history [cerebral infarction, myocardial infarction, thromboembolism, other]

Medical history (previous fracture) [no, yes]

Disposition of medical history (previous fracture) [vertebra, femur, wrist, forearm, upper arm, pelvis, lower limb, other]

Previous steroid use [no, yes]

Disposition of previous steroid use [at least 3 months at a prednisolone equivalent dose of 5 mg/day or more, otherwise, unknown dose]

| | |
|---------------------|--|
| | Parental history of femur fracture [no, yes] |
| | Drinking history [no, yes] |
| | Smoking history [never smoked, current smoker, past smoker] |
| | Duration of Benet/Actonel treatment (months) [*] [<12, ≥12 to <24, ≥24 to <36, ≥36] |
| | Amount of Benet/Actonel administered (mg) [*] [<900, ≥900 to <1800, ≥1800 to <2700, ≥2700] |
| | Presence or absence of previous treatment [no, yes] |
| | Disposition of previous treatment [osteoporosis drug, anti-inflammatory analgesic, cardiovascular drug, central nervous system drug, antidiabetic, digestive system drug, other] |
| | Switching group [Benet/Actonel 2.5 mg, Benet/Actonel 17.5 mg, bisphosphonate other than Benet/Actonel, calcium alone, vitamin D alone, combination of calcium and vitamin D, osteoporosis drug not listed above, steroid, other] |
| | Presence or absence of concomitant medication [no, yes] |
| | Disposition of concomitant medication [osteoporosis drug, anti-inflammatory analgesic, cardiovascular drug, central nervous system drug, antidiabetic, digestive system drug, other] |
| | Combination therapy group [Benet/Actonel 75 mg alone, calcium, vitamin D, combination of calcium and vitamin D, osteoporosis drug not listed above, steroid, other] |
| | Presence or absence of physical therapy [no, yes] |
| | Presence or absence of other concomitant therapy [no, yes] |
| | Presence or absence of low back pain at the start of treatment [no, yes] |
| 4) Analysis methods | The number and proportion of patients will be calculated for the analysis item. Summary statistics will be calculated for analysis items with *. |

6.1.3. Treatment Compliance Status

| | |
|---------------------|--|
| 1) Analysis set | Patients included in safety analysis |
| 2) Chart plan | Table 1-3 |
| 3) Analysis item | Treatment status [took the drug as instructed by a physician, took the drug on a different day from instructed by a physician, took no dose, unknown] |
| 4) Analysis methods | The number and proportion of patients will be calculated for the analysis item by the number of doses. In addition, a stacked bar chart will be plotted with the percentage of number of patients on the vertical axis and |

the number of doses on the horizontal axis.

6.1.4. Changes in Treatment Compliance Rate over Time

- | | |
|---------------------|---|
| 1) Analysis set | Patients included in safety analysis |
| 2) Chart plan | Table 1-4 |
| 3) Analysis item | Treatment compliance rate |
| 4) Analysis methods | Summary statistics will be calculated for the analysis item by the number of doses. In addition, a line chart will be plotted with the treatment compliance rate on the vertical axis and the number of doses on the horizontal axis. |

6.1.5. Changes in Dosing Interval over Time

- | | |
|---------------------|---|
| 1) Analysis set | Patients included in safety analysis |
| 2) Chart plan | Table 1-5 |
| 3) Analysis item | Dosing interval |
| 4) Analysis methods | Summary statistics will be calculated for the analysis item by the number of doses. In addition, a line chart will be plotted with the dosing interval on the vertical axis and the number of doses on the horizontal axis. |

6.2. Analysis of Safety

The safety will be analyzed in patients included in safety analysis.

6.2.1. List of Occurrence of Adverse Drug Reactions (Attachment Style 2)

- | | |
|---------------------|---|
| 1) Analysis set | Patients included in safety analysis |
| 2) Chart plan | Table 2-1 |
| 3) Analysis items | Number of surveillance sites Number of surveyed patients Number of patients with an ADR, etc. Number of ADRs, etc. Proportion of patients with an ADR, etc. Proportion of patients with an ADR, etc. (number of ADRs, etc.) by type (PT) |
| 4) Analysis methods | The number and proportion of patients (number of events) will be calculated for the analysis item, and a list of occurrence of ADRs will be prepared. |

6.2.2. List of Occurrence of Serious Adverse Events (Attachment Style 2-2, Attachment Style 10)

- | | |
|---------------------|--|
| 1) Analysis set | Patients included in safety analysis |
| 2) Chart plan | Table 2-2 |
| 3) Analysis items | Number of surveillance sites Number of surveyed patients Number of patients with a SAE Number of SAEs Proportion of patients with a SAE Proportion of patients with a SAE (number of SAEs) by type (PT) |
| 4) Analysis methods | The number and proportion of patients (number of events) will be calculated for the analysis item, and a list of occurrence of SAEs will be prepared. |

6.2.3. Occurrence of Adverse Events by Type

- | | |
|---------------------------|--|
| 1) Analysis set | Patients included in safety analysis |
| 2) Chart plan | Table 2-3 |
| 3) Analysis item | AE type (SOC, PT) |
| 4) Classification factors | Relationship [yes, no] Seriousness [serious, not serious] Time of onset [Days 1-7, Days 8-14, Days 15-21, Days 22-28, Days 29-56, Days 57-84, Days 85-180, Days 181-210, Days 211-360, Day 361 or later], [Days 1-3, Days 4-14, Days 15-30, Days 31-90, Days 91-180, Days 181-270, Days 271-360, Day 361 or later] Presence or absence of discontinuation of Benet/Actonel treatment [yes, no] Outcome [recovered, recovering, not recovered, recovered with sequelae, death, unknown] |
| 5) Analysis methods | The number of patients will be calculated by AE type for each category of classification. |

6.3. Analysis of Efficacy

The efficacy will be analyzed in patients included in efficacy analysis. Patients with no pre- or post-baseline data on the relevant efficacy endpoint will be excluded from analysis.

6.3.1. Incidence of Vertebral Fracture

- | | |
|-----------------|--|
| 1) Analysis set | Patients included in efficacy analysis |
|-----------------|--|

| | |
|---------------------|---|
| 2) Chart plan | Table 3-1-1-1 Table 3-1-1-2 Table 3-1-2-1 Table 3-1-2-2 Table 3-1-3-1 Table 3-1-3-2 |
| 3) Analysis items | New vertebral fracture or worsening of prevalent fracture New vertebral fracture or worsening of prevalent fracture <non-traumatic> New vertebral fracture New vertebral fracture <non-traumatic> Worsening of prevalent fracture Worsening of prevalent fracture <non-traumatic> |
| 4) Analysis methods | Using the Kaplan-Meier method with the first onset of the analysis item as the event, the number of relevant patients (risk population), number of censored patients, number and proportion of patients with event, as well as the point estimate of cumulative incidence, standard error, and 95% confidence interval, at each time point of assessment will be calculated. In addition, a Kaplan-Meier curve will be plotted with the cumulative incidence (%) on the vertical axis and the time (months) on the horizontal axis. |

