4.0 Surveillance Population

Osteoporotic patients will be included in the surveillance. The selection criteria listed below should also be met, and the precautions concerning indications in the package insert should be referred to.

Selection criteria

Patients meeting all of the following criteria will be included in the surveillance:

- 1) A patient with evidence of 1 to 4 fractures from the fourth thoracic vertebra to the fourth lumbar vertebra (T₄ to L₄) provided by thoracic and lumbar spinal radiography performed before the start of the surveillance (within 3 months before the start of prescription of Benet)
- 2) A patient aged 50 years or older (menopausal if female)
- 3) An outpatient who can walk

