10.6 Analysis Methods

- 1) For vertebral fracture and non-vertebral fracture, the number and proportion of patients with fracture and cumulative incidence at each time point, including the final time point, will be calculated.
- 2) For the other endpoints, significance test will be performed by one-sample t-test, one-sample Wilcoxon test, or chi-square test, depending on the nature of the analysis item.

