5.2. Handling of Adverse Events

Multiple episodes of the same AE/ADR (SOC) in the same patient will be tabulated as 1 patient.

Multiple episodes of the same AE/ADR (PT) in the same patient will be tabulated as 1 event.

For tabulation by type (seriousness, time of onset, outcome), multiple episodes of the same AE/ADR (PT) in the same patient will be tabulated as 1 event on a PT basis according to the following order of precedence:

Seriousness: serious > not serious

Time of onset: chronological order

Outcome: death > recovered with sequelae > not recovered > recovering > recovered > unknown

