6.3.1. Incidence of Vertebral Fracture

| | |
|---------------------|--|
| 1) Analysis set | Patients evaluated for efficacy with dates of pre- and post-treatment ^{*1} radiography Patients evaluated for vertebral fracture |
| 2) Chart plan | Table 3-1-1-1 Table 3-1-1-2 Table 3-1-1-3 Table 3-1-1-4 Table 3-1-1-5 Table 3-1-1-6 Table 3-1-2-1 Table 3-1-2-2 Table 3-1-2-3 Table 3-1-2-4 Table 3-1-2-5 Table 3-1-2-6 |
| 3) Analysis items | New vertebral fracture or worsening of prevalent fracture New vertebral fracture or worsening of prevalent fracture <non-traumatic> New vertebral fracture New vertebral fracture <non-traumatic> Worsening of prevalent fracture Worsening of prevalent fracture <non-traumatic> |
| 4) Analysis methods | For the time to the first onset of the analysis item, the point estimate of cumulative incidence, standard error, and 95% confidence interval will be calculated using the Kaplan-Meier method, and the number of relevant patients (number of patients at risk), cumulative number of patients with |

the analysis item, and cumulative number of censored patients at Month 6 (Day 180), Month 12 (Day 360), Month 18 (Day 540), Month 24 (Day 720), Month 30 (Day 900), and Month 36 (Day 1096) will be calculated. In addition, a Kaplan-Meier curve will be plotted with the cumulative incidence (%) on the vertical axis and the time (months) on the horizontal axis. The number of relevant patients (number of patients at risk) will be presented under the time (months).

The time to the first onset of the analysis item is defined as time from the start date of Benet/Actonel treatment to the earliest date of radiography with a diagnosis of the analysis item. Patients with no analysis item will be censored at the latest date of radiography with no evidence of the analysis item.^{*2}

No radiographic data collected after the end date of Benet/Actonel treatment + 90 days or after 3 consecutive months (90 days) of interruption in patients with interruption of treatment will be used for analysis.

*1 Range of assessment before and after treatment

- Before treatment: before the start of Benet/Actonel treatment defined as Days -90 to 1
- After treatment: before the end date of Benet/Actonel treatment + 90 days, and before 3 consecutive months (90 days) of interruption in patients with interruption of treatment

*2 The date of radiography with no evidence of the analysis item is defined as follows for each analysis set:

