6.3.2. Incidence of Non-vertebral Fracture

| | |
|---------------------|---|
| 1) Analysis set | Patients evaluated for efficacy |
| 2) Chart plan | Table 3-2-1 Table 3-2-2 Table 3-2-3 Table 3-2-4 |
| 3) Analysis items | Non-vertebral fracture Non-vertebral fracture <non-traumatic> Femur fracture Femur fracture <non-traumatic> |
| 4) Analysis methods | Non-vertebral fracture will be analyzed in the same manner as described in Section 6.3.1, “Incidence of Vertebral Fracture.” The time to the first onset of the analysis item is defined as time from the start date of Benet/Actonel treatment to the earliest date of diagnosis of the analysis item. Patients with no analysis item will be censored at the latest date of dosing, discontinuation, assessment of each efficacy endpoint, or onset/outcome of AE. |

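### The fracture figure called cumulative incidence is one minus Kaplan-Meier with deaths left as ordinary censoring, so it estimates on-treatment risk in the absence of death; the effect is small and cheap to show.

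*SAP*

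**What the plan says.** The operative text is SAP 5.1. For vertebral fracture, section 6.3.1 states that "the point estimate of cumulative incidence, standard error, and 95% confidence interval will be calculated using the Kaplan-Meier method". SAP versions 2.0 to 4.1 put the same method as "Using the Kaplan-Meier method with the first onset of the analysis item as the event". On censoring, SAP 5.1 says: "Patients with no analysis item will be censored at the latest date of radiography with no evidence of the analysis item". Films taken more than 90 days after the end of treatment, or after a 90-day interruption, are not used. Both analysis sets in 6.3.1 require a dated film before treatment and another after it (see also section 4.5, criterion 4).

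Section 6.3.2 applies the same method to non-vertebral and femur fracture, with its own censoring rule: "Patients with no analysis item will be censored at the latest date of dosing, discontinuation, assessment of each efficacy endpoint, or onset/outcome of AE".

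Death appears in the SAP only as an adverse event outcome. Section 5.2 ranks outcomes as "Outcome: death > recovered with sequelae > not recovered > recovering > recovered > unknown", and section 6.2.3 tabulates them. No section names death as a competing event or says that the fracture estimate is conditional on nobody dying.

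Protocol section 10.6 asks for more than one measure: "the number and proportion of patients with fracture and cumulative incidence at each time point, including the final time point, will be calculated". SAP 5.1 section 6.3.1 lists the numbers at risk, with the event and censored, but no crude proportion. Section 6.3.3 adds vertebral fracture rates per 100 person-years.

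**The concern.** A patient who has died cannot fracture. One minus Kaplan-Meier treats a censored patient as still exposed to the same fracture risk as those who remain. When the reason for censoring is death, the curve describes a setting in which nobody dies. In 6.3.2 the date of a fatal adverse event outcome can itself be the censoring date. In 6.3.1 a patient who dies after at least one negative follow-up film is censored at the last such film.

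This matters because the surveillance has no control group and its stated aim is fracture incidence over 36 months in clinical settings, so an absolute risk is its main result. Eligible patients are 50 or older with one to four vertebral fractures, and the baseline table in SAP 6.1.2 splits age at 75, so some deaths are to be expected. The Kaplan-Meier value is the only percentage risk that 6.3.1 and 6.3.2 name, and its label does not say which risk it is.

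**Working it through.** **Inputs from the documents.** Observation period 36 months (Protocol 7.1); about 250 patients needed, 50% dropout, 500 enrolled (Protocol 3.2); last read-out Day 1096 (SAP 6.3.1). The one derived figure in the plan reproduces: 250 / (1 − 0.5) = 500. The documents state no fracture rate, mortality or precision.

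**Assumptions.** Constant hazards; 36-month fracture risk F in the absence of death; 36-month mortality D.

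**Step 1: size of the death component.** Let a = −ln(1 − F) and b = −ln(1 − D). Kaplan-Meier targets F. With death as a competing event the cumulative incidence is

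CIF = a/(a + b) × [1 − (1 − F)(1 − D)].

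- F = 10%, D = 3%: 0.10536/0.13582 × (1 − 0.90 × 0.97) = 0.7757 × 0.127 = 9.85%.
- F = 20%, D = 10%: 0.22314/0.32850 × (1 − 0.80 × 0.90) = 0.6793 × 0.28 = 19.02%.

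| Assumed D | CIF when F = 10% (excess, points) | CIF when F = 20% (excess, points) | Relative excess |
|---|---|---|---|
| 3% | 9.85% (0.15) | 19.71% (0.29) | about 1.5% |
| 6% | 9.70% (0.30) | 19.42% (0.58) | about 3% |
| 10% | 9.50% (0.50) | 19.02% (0.98) | about 5% |
| 20% | 8.98% (1.02) | 18.00% (2.00) | about 11% |

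**Step 2: compare with the precision.** Take 500 patients with exponential dropout reaching 50% at 36 months, so c = −ln 0.5 = 0.69315. The Greenwood variance is

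(1 − F)² × a × [1/((1 − F) × 0.5) − 1] / (a + c) / 500.

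- F = 10%: 0.81 × 0.10536 × 1.2222 / 0.79851 / 500 = 0.000261; standard error 1.62 points, half-width 3.17 points.
- F = 20%: standard error 2.16 points, half-width 4.24 points.

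For mortality up to 10%, the excess is well inside the interval.

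**Step 3: film timing in 6.3.1.** Vertebral fractures are dated by films, so the censoring and read-out rules were simulated. The assumptions were yearly films with a 30-day standard deviation, a film at half of discontinuations, 50% dropout and F = 10%.

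| Assumed D | Scheduled films only, Day 1096 | 30% of fractures filmed at onset | True CIF |
|---|---|---|---|
| 3% | 9.83% | 10.16% | 9.85% |
| 10% | 9.97% | 10.30% | 9.50% |

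The simulated figures move in the first decimal place from run to run, so only the pattern should be read. A Month 36 film taken after Day 1096 is not counted in the read-out, which pulls the figure down. Films taken on suspicion, combined with censoring at the last negative film, push it up. At 3% mortality the net excess can vanish; at 10% it persists.

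**Step 4: early deaths in 6.3.1.** Films are scheduled at 12, 24 and 36 months (Protocol 9.2.5). A patient who dies before any follow-up film is outside both 6.3.1 sets: excluded, not censored. In a further simulation with annual and exit films, 50% dropout and D = 10%, including or excluding these patients moved the Aalen-Johansen estimate by about 0.3 points at F = 10% and 0.6 at F = 20%. The correction itself is 0.5 to 1.0 points, so the number of such patients has to be reported.

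**The case against.** The case against runs as follows. Under independent censoring Kaplan-Meier is a valid estimate of risk in the absence of death, and the SAP never says it wants anything else. The data rules already make the result an on-treatment quantity. Eligible patients are outpatients who can walk, and nothing in the documents shows that mortality will be high. The excess is small beside the confidence interval. Censoring from the expected 50% dropout, if informative, is probably the larger problem, and an Aalen-Johansen estimate that still censors discontinuation does not touch it. The plan also offers other views: numbers with event and censored, vertebral rates per person-year, a listing of discontinued patients with reasons and adverse events, and the crude proportion that the Protocol requires.

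Most of this stands, and it limits the point to a minor one. It does not remove it. None of the other outputs is a percentage risk that allows for death. The crude proportion is lowered by dropout, and the person-year rate is not a risk and covers vertebral fracture only. If the risk in the absence of death is what is wanted, the label should say so. The objection does rule out replacing the headline method; a second estimate beside it is enough.

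**Conclusion.** The point holds as a minor one. In SAP 5.1 sections 6.3.1 and 6.3.2 the quantity called cumulative incidence is on-treatment fracture risk in the absence of death. For the risk in a population that can die, the death component is biased upward by about 1.5%, 3% and 5% in relative terms at assumed 3-year mortality of 3%, 6% and 10%. At 10% to 20% fracture risk that is 0.15 to 0.98 points. These sizes rest on constant hazards and on mortality and fracture risks that the documents do not give. That deaths are censored follows from the SAP's silence, since the stated rules leave no other treatment.

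A reader might infer that the reported incidence will be too high as a matter of fact, and that the error always runs upward. The documents do not support either. They contain no mortality figure, the excess exists only relative to a target the SAP does not state, and for vertebral fracture at Month 36 film timing and the Day 1096 read-out can cancel it. The case is cleanest for non-vertebral and femur fracture in 6.3.2, where no film dates or film-based exclusions intervene.

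**What to change.** 1. In 6.3.2 add an Aalen-Johansen estimate, with standard error and 95% confidence interval at the same days as the Kaplan-Meier estimate. Treat death within the allowed data period as a competing event, dated by the recorded fatal adverse event outcome, and keep discontinuation as censoring. By SAP 5.4 and 5.5 the period runs to 30 + 90 = 120 days after the last recorded dose, subject to the 90-day interruption rule.
2. Do the same in 6.3.1. State that patients who die before any post-treatment film are outside the analysis set, and report how many there are.
3. Show the new estimate beside the existing Kaplan-Meier figure, with the number of deaths before fracture.
4. Label the Kaplan-Meier figure as risk in the absence of death.

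The cost is SAP wording and one extra standard analysis on data already collected. There are three downsides. Two figures appear where there was one. Protocol 9.3 records a date of outcome assessment rather than an explicit date of death, so some deaths will be dated approximately. And the change does nothing about possibly informative censoring from the expected 50% dropout, which needs its own treatment.
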